2.2.1 Subgroup of interest

Subgroup analyses of the two primary efficacy variables and the secondary endpoint of absolute change from baseline in LDL-C will be performed for the following subgroups (note that results for a subgroup category will only be presented if the total across both treatment groups within the category is at least 10 participants):

- Background lipid-lowering therapy at baseline: Yes, No
- Medical history of statin intolerance: Yes, No (from medical history statin intolerance CRF page; do not use this subgroup for the co-primary efficacy endpoint discontinuation of statin therapy)
- Baseline statin intensity: High, Moderate or Low, None
- Age: <65 years, ≥ 65 years
- Baseline LDL-C: ≤100 and > 100 mg/dL; median; and then by quartiles
- Most recent ASCVD event: <1 year, ≥ 1 year (from targeted medical history CRF page, see below for more details)
- Diabetes at baseline: Yes, No (from targeted medical history CRF page)
- Renal impairment by eGFR categories at baseline: <15, ≥15 to <30, ≥30 to <60, ≥60 to <90, or ≥90 mL/min/1.73m²
- Sex: Male, Female
- Race: White, Non-White/Multiple (unknown will be excluded from subgroup analyses)
- Ethnicity: Hispanic or Latino, Not Hispanic or Latino (unknown or not reported will be excluded from subgroup analyses)
- [REDACTED]
- Coronary heart disease (CHD): Yes, No (from targeted medical history CRF page)
- Peripheral artery disease (PAD): Yes, No (from targeted medical history CRF page)
- Cerebrovascular disease (CVD): Yes, No (from targeted medical history CRF page)
- Polyvascular disease (>1 of CHD, PAD, or CVD): Yes, No (from targeted medical history CRF page)
- [REDACTED]

Most recent ASCVD event (<1 year, ≥ 1 year) is derived from data recorded on the “Medical History Targeted” form. The derivation is based on the timing of the most recent percutaneous coronary intervention, myocardial infarction, cardiovascular arterial bypass graft, or ischemic stroke. If a participant has multiple events with different timings, the earlier (<1 year) timing will be utilized. Participants without events are excluded from the subgroup.

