For primary efficacy variable 2, a one-sided 98.75% confidence interval for treatment difference ("inclisiran first" implementation strategy – usual care) in the proportion of participants who discontinued statin therapy at Day 330 will be computed using the normal approximation to the binomial distribution. Non-inferiority of the "inclisiran first" implementation strategy to usual care will be declared if the upper limit of the confidence interval does not exceed the non-inferiority margin of 0.15. The difference in proportions and associated two-sided 97.5% confidence interval will also be provided.

The primary analysis of primary efficacy variable 2 will be based on the FAS excluding participants who had medical history of statin intolerance. The primary analysis of this variable will be repeated for the Per-Protocol Set and Restricted Set 2.

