For primary efficacy variable 2, i.e., discontinuation of statin therapy (yes, no), a z-test for a non-inferiority test of two proportions, an allocation ratio of 1:1, and a one-sided significance level of 0.0125 were used in the calculation of sample size. Table 3-2 considers total sample sizes for 0.20 and 0.25 as the true proportions of participants who discontinue statin therapy in each treatment group, and non-inferiority margins of 0.10 and 0.15 for the "inclisiran first" implementation group to be no worse than the usual care group (nQuery Version 8.4.1.0). From Table 3-2, a true proportion of 0.20 for participants who discontinue statin therapy in each treatment group by Day 330, a non-inferiority margin of 0.15, and a power of 0.90 were chosen to provide a total sample size of 354 participants.

Table 3-2 Sample Size Calculations for Statin Statin Therapy Discontinuation

Proportion in usual care group	Non-inferiority margin	Power = 0.85	Power = 0.90
0.20	0.10	688	796
0.20	0.15	306	354
0.25	0.10	806	932
0.25	0.15	360	414

Based on the sample size calculations in Table 3-1 and Table 3-2, a total sample size of 354 together with a loss to follow-up rate of 10% at Day 330 and a statin intolerance rate at baseline of 10% (i.e., a total of 20% due to loss to follow-up and statin intolerance at baseline) require

approximately 444 participants (222 participants per treatment group) to be randomized. This will also allow examination of subgroups with reasonable sample sizes.

4 Change to protocol specified analyses

Changes from Protocol version 01 (amended protocol) include the following:

1. Protocol Section 12.4.2 states that an unstructured working correlation matrix will be assumed for the MMRM. An unstructured covariance matrix will be used instead.
2. The protocol uses Day 0 as the first inclisiran dose day. In order to aid in counting of dosing days the first dose day will be referred to as Day 1.

Changes from Protocol version 02 (amended protocol) include the following:

3. Protocol Section 12 notes that the interquartile range will be provided. In order to streamline the tables this statistic was removed.
4. Protocol Section 12.2 notes that relevant medical histories and current medical conditions at baseline would be summarized using the Safety Set, the FAS was used instead.

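### Statin-discontinuation subgroups are shown from 10 participants in total, and the only interval supplied, the normal approximation, can collapse to zero width or under-cover in the smallest categories

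*SAP*

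**What the plan says.** SAP 2.2.1 states that "Subgroup analyses of the two primary efficacy variables and the secondary endpoint of absolute change from baseline in LDL-C will be performed" for a long list of factors. The display rule is that "results for a subgroup category will only be presented if the total across both treatment groups within the category is at least 10 participants". The rule counts both arms together and sets no minimum per arm or number of events.

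For statin discontinuation, SAP 2.5.2 specifies "a one-sided 98.75% confidence interval for treatment difference" and says that the difference in the "proportion of participants who discontinued statin therapy at Day 330 will be computed using the normal approximation to the binomial distribution". It adds: "The difference in proportions and associated two-sided 97.5% confidence interval will also be provided". Non-inferiority "will be declared if the upper limit of the confidence interval does not exceed the non-inferiority margin of 0.15". These sentences describe the primary analysis.

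Neither document names another interval for subgroups or a rule for sparse or zero cells. SAP 5.4.1, where model detail for the primary objective could have stood, is marked not applicable. The 2.5.2 interval is therefore the only one available to whoever programs the subgroup tables.

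**The concern.** The normal-approximation (Wald) interval estimates its variance from the observed proportions. When those are 0 or 1 the estimated variance is 0, however few people were observed. A floor of 10 in total lets such tables through. A category of five per arm with no discontinuations would be printed with a difference of 0 and an interval of zero width, next to categories whose limits are being compared by eye with 0.15. The least informative category would look the most precise. Where the interval does not collapse completely, it can still be too narrow at these sizes. At stake is how subgroup displays of a primary endpoint are read, not the trial's primary conclusion.

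**Working it through.** **Inputs.** Planned discontinuation 0.20 in each arm, margin 0.15, one-sided 0.0125, power 0.90, 354 evaluable, 444 randomized, 10% statin-intolerant at baseline (SAP 3). Display floor of 10 in total (SAP 2.2.1). z(0.9875) = 2.2414, z(0.90) = 1.2816. Usual-care rates of 10% and 5% below are assumptions, used to show the range.

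**1. The plan's own figure.** With unpooled variance, n per arm = (2.2414 + 1.2816)² × 2 × 0.20 × 0.80 / 0.15² = 12.41 × 14.22 = 176.5, so 177 per arm and 354 in total, as stated. The same formula reproduces all eight cells of SAP Table 3-2.

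**2. The Wald interval in a 10-person category.** d ± 2.2414 × √[p1(1−p1)/n1 + p2(1−p2)/n2].

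- 0/5 v 0/5: 0 ± 2.2414 × 0, which is [0, 0].
- 5/5 v 5/5: also [0, 0].
- 0/5 v 1/5: −0.20 ± 2.2414 × √0.032, which is −0.601 to 0.201. One event is enough to avoid full collapse.
- 0/1 v 1/9 (inclisiran first v usual care): the single-person arm contributes no variance, and the upper limit is −0.111 + 2.2414 × 0.1048 = 0.12. A 9:1 split in either direction is rare: 20/1024 = 2.0% for ten people allocated 1:1.

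**3. A score interval on the same data.** With no events in either arm, the Miettinen-Nurminen upper limit solves d² = z² × d(1−d)/n × N/(N−1), with N = 2n. So d = k/(1+k), where k = z²N/[n(N−1)].

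- 5 per arm: k = 5.024 × 10/45 = 1.116, limit 0.53.
- 10 per arm: k = 5.024 × 20/190 = 0.529, limit 0.35.
- The limit first reaches 0.15 or less at 29 per arm (58 in total).

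**4. How often there are no events at all, at 20% in both arms.** 0.8¹⁰ = 10.7% for 10 people, 0.8²⁰ = 1.2% for 20, and 0.8⁴⁰ = about 0.01% for 40.

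**5. How often the Wald upper limit is at or below 0.15 when the true difference is exactly 0.15.** This is an exact sum of the binomial probabilities over all tables meeting the condition. The nominal figure is 1.25%.

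| Usual-care rate | 5 per arm | 10 per arm | 20 per arm |
|---|---|---|---|
| 20% (planned) | 7.1% | 2.4% | 1.6% |
| 10% (assumed) | 16.0% | 5.9% | 2.1% |
| 5% (assumed) | 26.1% | 10.8% | 2.7% |

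Miettinen-Nurminen at 5 per arm gives 0.9%, 0.2% and 0.04%. In the planned-rate case with 5 per arm, the table with no events in either arm has probability 0.65⁵ × 0.80⁵ = 3.8%, about half of the 7.1%. The rest comes from tables such as 0/5 v 2/5, whose upper limit is −0.40 + 2.2414 × √0.048 = 0.09.

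**6. The primary analysis.** Removing 10% statin-intolerant from 444 leaves about 400, or 200 per arm. By the same enumeration, the Wald type I error is 0.0126 at a usual-care rate of 20%, 0.0137 at 10% and 0.0160 at 5%. Miettinen-Nurminen gives 0.0126, 0.0123 and 0.0114. Power at 20% in both arms is 0.934 with Wald and 0.932 with Miettinen-Nurminen.

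**The case against.** The strongest reply is that the exposure is small and the plan makes no claim from it. Most of that stands.

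- **No subgroup decision.** A reader might infer that a small category could be declared non-inferior. The documents do not support that: the 0.15 rule belongs to the primary analysis, and SAP 2.2.1 attaches no test or decision to subgroups. Even the use of the Wald interval there is inferred from silence.
- **Few small categories.** With about 400 participants, two-way splits and LDL-C quartiles (about 100 each) are far above 10. eGFR categories below 30 are largely closed off by inclusion criterion 6 and would probably fall under the existing floor.
- **Zero events are made rarer by the endpoint definition.** SAP 2.5.1 scores every early terminator as having discontinued.
- **The primary interval.** A reader might infer that the primary test is unsound. At the planned rate it is not. The lower rates fit poorly with 10% planned loss to follow-up being scored as events.
- **LDL-C subgroups.** The same floor admits an unstructured four-visit model on ten people. Such a model might not converge or might be unstable, but no calculation shows that it would look falsely precise, so it is not part of this point.

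The reply does not remove the problem. Some small categories are foreseeable. Once statin-intolerant participants are excluded, baseline statin intensity None should be nearly empty, because inclusion criterion 7 requires maximally tolerated statin therapy otherwise. Anyone there who never starts a statin would apparently count as discontinued, so all-event cells, which also give [0, 0], are plausible. The floor of 10 shows that the SAP meant to screen out uninformative categories, and it does not do so.

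**Conclusion.** The point holds as a minor but real defect in how subgroup results for statin discontinuation would be displayed. At the smallest size the SAP permits, the only interval supplied is degenerate in 10.7% of categories through zero events alone, if the rate is 20% in both arms. With 5 per arm its upper limit falls at or below 0.15 in 7.1% of cases where the true excess is 15 points over 20%. This shrinks to 2.4% at 10 per arm and 1.6% at 20. The figure of 16.0% at 5 per arm needs a usual-care rate of 10%, half the planned rate, and should not be read as the expected size.

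The conclusion assumes that the 2.5.2 interval is reused in subgroups and that some category close to the floor occurs. The primary non-inferiority conclusion is not affected at the planned rate.

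**What to change.** In SAP 2.2.1:

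1. Name the Miettinen-Nurminen score interval for subgroup differences in statin discontinuation, at the confidence level already used.
2. Replace the total-of-10 rule with a minimum per arm, and show counts only below it. Twenty per arm is one example. The number is a judgement and is not derived here.
3. State that subgroup limits are descriptive and are not tests against 0.15.

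Using the same score interval for the primary analysis in SAP 2.5.2 is optional. It would hold the error rate closer to or below nominal if discontinuation proved lower than planned, and would cost about 0.2 points of power (0.934 to 0.932 at 200 per arm). It would also depart from the unpooled z-test used for sizing.

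The cost is SAP and table-shell wording and a software option, with no new data or sample size. The downside is that a few small categories would appear as counts without an estimate.

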2.3 Patient disposition, demographics and other baseline characteristics

Summary statistics will be presented for continuous demographic and baseline characteristics and the number and percentage of participants in each category will be presented for categorical variables for each treatment group. The summaries will be reported for the FAS, if not otherwise stated.

2.3.1 Patient disposition

Participant disposition will be summarized as follows:

- The number of participants who signed the informed consent form, are screen failures, are randomized, are treated (Safety Set), completed the study or who discontinued early along with reasons for early study discontinuation, the number of screened subjects, completed screening phase and were randomized, completed screening phase but were not randomized, did not complete screening phase, and primary reason for not completing screening phase will be summarized for all screened participants.
- The number of participants in each analysis population along with reasons for exclusion from each analysis population will be summarized by treatment group for all randomized participants.
- The number of participants who completed the study or who discontinued early along with reasons for early study discontinuation will be summarized by treatment group for the FAS.
- The duration on study (number of days from study start date to study end date [last recorded contact/participation date in the database]) will be summarized by treatment for the FAS.

A summary of failed inclusion/exclusion criteria will be provided for all screened participants and by treatment group for the FAS.

A summary of the number of participants by visit will be provided by treatment group for the FAS.

The number and percentage of participants with important protocol deviations will be summarized by treatment group for the FAS.

2.3.2 Demographics and other baseline characteristics

Participant demographics including age, age category (<65 years vs ≥65 years; 18 to <50, 50 to <65, 65 to <75, ≥75 years), race, ethnicity, sex, and child bearing potential status; and baseline characteristics such as insurance type, income level, highest completed education, smoking

status by substance, body height, weight, [REDACTED] will be summarized by treatment for the FAS.

Medical history (targeted medical history, other medical history, and medical history of statin intolerance) will be summarized by treatment group using the FAS. Other medical history will be summarized by system organ class and preferred term.

2.4 Treatments (study treatment, rescue medication, concomitant therapies, compliance)

2.4.1 Study treatment / compliance

Study drug administration will be summarized overall for the Safety Set.

2.4.2 Prior, concomitant and post therapies

Concomitant medications and significant non-drug therapies prior to and after study treatment start date will be listed and summarized according to the Anatomical Therapeutic Chemical (ATC) classification system and preferred drug name, by treatment group, for the Safety Set. Additional summaries will be provided for lipid-lowering therapies. See list of lipid-lowering therapies below. Medications will be coded using the World Health Organization (WHO) drug dictionary (WHODDG March 2021, B3 format) initially, and will be coded/re-coded with up-version during the course of study.

Prior medications include all medications stopped prior to study treatment start date. Concomitant medications include any medications taken on or after study treatment start date.

The statin intensity (none, low, moderate, high) will be defined by clinical review of the data according to American College of Cardiology/American Heart Association (ACC/AHA) classification of high intensity and based on the specific statin drug name, dose (unit), and frequency recorded in the data.

Lipid-lowering therapies (LLT) taken at baseline, changes in lipid-lowering therapies prior to baseline, concomitant lipid-lowering therapies post baseline, a shift table from baseline statin intensity level to post-baseline lipid-lowering therapy addition group, and a shift table for statin intensity from baseline (study Day 1) to Day 330/End of Study (EOS) will also be provided. The statin intensity of the last statin taken on or prior to Day 330 (EOS) will be used for the post-baseline statin intensity.

For the analysis of lipid-lowering therapies at baseline a modified lipid-lowering therapy definition is also employed. For this analysis a modified lipid lowering therapy includes any statin, ezetimibe, PCSK9 inhibiting monoclonal antibodies, or bempedoic acid therapies.

The following medications will be included in the lipid-lowering therapy tables.

Medication	Medications included
Lipid Lowering Therapy	ATCCODE2=C10
Statin	ATCCODE2=C10 and CMDECOD contains 'statin'

Ezetimibe	ATCCODE2=C10 and CMDECOD contains 'ezetimibe'
PCSK9 inhibiting monoclonal antibodies	ATCCODE2=C10 and CMDECOD contains 'evolocumab' or 'alirocumab'
Bempedoic acid	ATCCODE2=C10 and CMDECOD contains 'bempedoic acid'
Modified lipid lowering therapy	ATCCODE2=C10 and CMDECOD contains 'statin', 'ezetimibe', 'evolocumab', 'alirocumab', or 'bempedoic acid'

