#### 4.1.1 Rationale for choice of background therapy

Participants are required to be on maximally tolerated statin therapy at the time of identification and screening without plans to adjust lipid lowering therapy at that point in time.

Other than inclisiran in the inclisiran arm, therapies will not be made available by the sponsor. The trial could be criticized if patients in the usual care arm could not receive non-statin therapies because of insurance issues. To address the bias that may arise due to differences in access to therapies, randomization will be stratified by [REDACTED] as described in [Section 6.3.2](#) of the protocol, and various statistical methods will adjust for [REDACTED] at baseline (yes, no). Importantly, valuable insights can be gathered from studying the implementation of an “inclisiran first” implementation strategy versus usual care without providing access to therapies:

- It increases the external validity of the trial
- It enables the study of implementation of an effective LDL-C lowering therapy in the absence of access barriers
- It enables examination of implementation of inclisiran in [REDACTED]

Inclisiran will not be excluded from the comparator group post-approval to avoid withholding of an approved therapy if deemed necessary by the treating physician, although the use of inclisiran in the comparator group is discouraged. Inclisiran will not be provided by the sponsor to participants in the comparator group. It is assumed based on historical and anticipated product uptake shortly after launch that potential inclisiran treatment in the comparator group will be minimal and thus will not significantly interfere with the study. Participants receiving inclisiran during the trial should not be simultaneously treated with a PCSK9 inhibiting monoclonal antibody since simultaneous use has not been evaluated in registration trials.

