### **12.1 Analysis sets**

The Full Analysis Set (FAS) comprises all randomized participants. According to the intent-to-treat principle, participants will be analyzed according to the treatment group they have been assigned to during the randomization procedure.

The Per-Protocol Set is a subset of the Full Analysis Set in which participants are not treated with any inclisiran if they are randomized to the usual care treatment group or do not have any major protocol deviations (including deviations from inclusion/exclusion criteria) in either treatment group.

The Restricted Set 1 is a subset of the Full Analysis Set, which includes only participants without changes in background lipid-lowering therapy.

The Restricted Set 2 is a subset of the Full Analysis Set, which includes only participants who received three doses of inclisiran in the “inclisiran first” implementation strategy group (i.e., excludes patients in the “inclisiran first” implementation strategy group who missed one or more doses) and all participants in the usual care group (including participants who may have used commercially available inclisiran).

The Safety Set includes all participants who received study treatment. Participants will be analyzed according to the study treatment received at randomization.

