## **12.3 Treatments**

Concomitant medications and significant non-drug therapies prior to and after the start of treatment will be listed and summarized according to the Anatomical Therapeutic Chemical (ATC) classification system, by treatment group, for the Safety Set.

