2.1.1 General definitions

Study Treatment

The following are the investigational treatments:

- Inclisiran (KJX839), 284 mg, 1.5 ml liquid in a single-use prefilled syringe (PFS) for s.c. administration plus usual care
- Usual care alone

The following treatment labels will be used for all tables, listings and figures:

- Inclisiran First
- Usual Care

Study treatment start and end date

Study treatment start date is defined as the first date when a non-zero dose of study drug is administered for the inclisiran group. If a participant, who is randomized to the Inclisiran First group, does not take any study drug then treatment start date will be the randomization date.

For the usual care alone group the study treatment start date will be the randomization date.

“Day 1” will be used to identify study treatment start date for both treatments.

Study treatment end date is defined as the treatment phase completion date recorded on the “Treatment Disposition” CRF for inclisiran participants. For the usual care alone group, the study treatment end date is the last recorded contact/participation date in the database.

Study start and end date

Study start date is defined as the first date when a non-zero dose of study drug is administered for the inclisiran group. If a participant, who is randomized to the Inclisiran First group, does not take any study drug then study start date will be the randomization date.

For the usual care alone group the study start date will be the randomization date.

Study end date is defined as the date of last recorded contact/participation date in the database.

Planned and actual treatment definitions

Table 2-1 Planned and Actual Treatment Definitions

Randomized Treatment Group	Inclisiran Use Scenario During Study (Inclisiran Use Recorded as Study Treatment or Concomitant Medication)	Planned Treatment	Actual Treatment
Inclisiran First	Received at least one dose of inclisiran	Inclisiran First	Inclisiran First
Inclisiran First	Never received inclisiran	Inclisiran First	Usual Care
Usual Care	Received at least one dose of inclisiran	Usual Care	Inclisiran First
Usual Care	Never received inclisiran	Usual Care	Usual Care

Study day

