2.2 Analysis sets

The **Full Analysis Set** (FAS) comprises all randomized participants. According to the intent-to-treat principle, participants will be analyzed according to the treatment group they have been assigned to during the randomization procedure.

The **Per-Protocol Set** is a subset of the FAS in which participants are not treated with any incilisiran if they are randomized to the usual care treatment group, and do not have any major protocol deviations (including deviations from inclusion/exclusion criteria) in either treatment group.

The **Restricted Set 1** is a subset of the FAS which includes only participants without changes in background lipid-lowering therapy. A change includes starting a new lipid-lowering therapy or stopping an existing lipid-lowering therapy after the study treatment start date.

The **Restricted Set 2** is a subset of the FAS which includes only participants who received three doses of inclisiran in the “inclisiran first” implementation strategy group (i.e., excludes patients in the “inclisiran first” implementation strategy group who missed one or more doses) and all participants in the usual care group.

The **Safety Set** includes all participants who received study treatment. Participants will be analyzed according to the study treatment received. Refer to Table 2-1 for assignment of actual treatment for the different scenarios. Participants in the usual care treatment group who have data collected at the baseline visit will be included in the Safety Set.

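### No planned table shows post-baseline lipid-lowering therapy drug by drug by randomized arm, and the Safety Set grouping puts inclisiran use under Usual Care at zero by construction

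*SAP*

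**What the plan says.** - **Set for medication tables.** SAP 2.4.2 reports concomitant medication "by treatment group, for the Safety Set. Additional summaries will be provided for lipid-lowering therapies". The tables then described (lipid drugs at baseline, changes before baseline, drugs after baseline, baseline statin intensity against post-baseline add-on group, and statin intensity shift to Day 330) carry no other set. Protocol 12.3 likewise reports concomitant medication under the ATC "classification system, by treatment group, for the Safety Set".
- **Grouping.** SAP 2.2, on the Safety Set: "Participants will be analyzed according to the study treatment received. Refer to Table 2-1 for assignment of actual treatment for the different scenarios". Protocol 12.1 differs: "Participants will be analyzed according to the study treatment received at randomization".
- **Table 2-1 (SAP 2.1.1).** The usage column is headed "Inclisiran Use Recorded as Study Treatment or Concomitant Medication", so a commercial prescription counts. The crossover row reads: "Usual Care Received at least one dose of inclisiran Usual Care Inclisiran First". The last entry is the actual treatment. A participant randomized to Inclisiran First and never dosed has actual treatment Usual Care.
- **Rows.** The SAP 2.4.2 drug list has all of ATC C10, statin, ezetimibe, PCSK9 antibodies (evolocumab or alirocumab only), bempedoic acid, and a modified group pooling those four classes. Inclisiran is absent.
- **The result to be interpreted.** SAP 2.5.2 and 2.5.3 analyse LDL-C on the FAS as randomized and ignore inclisiran use in usual care as an intercurrent event.
- **Expectation.** Protocol 4.1.1 assumes that "potential inclisiran treatment in the comparator group will be minimal and thus will not significantly interfere with the study". It gives no rate.

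**The concern.** The trial compares two strategies, so lipid drugs started after randomization are part of what each strategy delivered. SAP 1.2.1 justifies the primary estimands on the ground that they capture changes in other medication. Protocol 12.8.1 sets the assumed LDL-C difference at 15 partly because usual care may add non-statin drugs, commercial inclisiran among them. Changes in background lipid-lowering therapy by strategy are also a secondary objective.

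A reader who asks why the LDL-C difference was large or small will turn to the lipid-lowering-therapy tables. Grouped by actual treatment, they do not describe the arms that were compared. Usual-care participants who received inclisiran are counted under Inclisiran First together with all their other lipid drugs, and the Usual Care column cannot contain an inclisiran user. At stake is the interpretation of the primary LDL-C result and the reporting of the secondary objective. The primary tests are not affected.

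**Working it through.** **Arm size.** Inputs from SAP Section 3: difference 15, SD 40, two-sided 0.025, power 0.90; for statin discontinuation, 0.20 in each group, margin 0.15, one-sided 0.0125, power 0.90.

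- LDL-C: 2 × (2.2414 + 1.2816)² × 40² / 15² = 176.5, so 177 per arm, 354 in total.
- Discontinuation: (2.2414 + 1.2816)² × (2 × 0.20 × 0.80) / 0.15² = 176.5, again 354 in total.
- Loss of 20%: 354 / 0.80 = 442.5, so 443, or 444 for equal arms: 222 per arm.

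The plan's figures reproduce. Only the 222 is used below.

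**Where crossovers fall.** Let k be the number of usual-care participants with at least one inclisiran dose. Assume that all 444 enter the Safety Set and that everyone in the inclisiran arm is dosed. By actual treatment the columns hold 222 + k (Inclisiran First) and 222 − k (Usual Care). By Table 2-1 the number of inclisiran users in the second column is 0 for every k. By randomized arm the same data give k/222. The rates below are assumptions.

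| Assumed use in usual care | k | Inclisiran First column | Usual Care column | Inclisiran users shown under Usual Care | By randomized arm, k/222 |
|---|---|---|---|---|---|
| 1% | 2 | 224 | 220 | 0 | 0.9% |
| 2% | 4 | 226 | 218 | 0 | 1.8% |
| 5% | 11 | 233 | 211 | 0 | 5.0% |
| 10% | 22 | 244 | 200 | 0 | 9.9% |
| 20% | 44 | 266 | 178 | 0 | 19.8% |

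If 2% of the inclisiran arm (4 people) were also never dosed, 2% crossover would give 222 + 4 − 4 = 222 in each column. The totals would match the randomized arms although eight participants had changed place.

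**What other outputs give by randomized arm.**

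| Output | Gives | Does not give |
|---|---|---|
| Exclusion reasons by analysis set (SAP 2.3.1, Table 5-1) | Usual-care participants given inclisiran (Per-Protocol reason); participants with any change in background therapy (Restricted Set 1 reason) | Which other drugs, when |
| Variable 22, FAS (SAP 2.6.1) | Statin intensity change | Any non-statin drug |
| Variable 23, FAS (SAP 2.6.1) | Days covered, four classes pooled | Individual drugs; inclisiran |
| Supplementary MMRM; Per-Protocol repeat (SAP 2.5.6, 2.5.2) | LDL-C effect with crossover data or participants removed | Any display of therapy |

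None tabulates post-baseline lipid-lowering therapy drug by drug by randomized arm.

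**The missing row is a second, separate gap.** A table without an inclisiran row says nothing about inclisiran. It does not show zero. If the add-on groups follow the listed rows, a participant who adds only commercial inclisiran has no drug category.

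**The case against.** Several objections carry weight.

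- **The set is inferred.** The sentence introducing the lipid-lowering-therapy summaries names no set. The FAS default in SAP 2.3 covers disposition and baseline summaries only, so the Safety Set is the natural reading of 2.4.2, but it is a reading. If the sponsor intends the FAS, saying so settles the grouping.
- **Crossover can be counted.** A reader might infer that the assumption of minimal comparator use cannot be tested. It can: the exclusion table should give the count by randomized arm. The SAP does not say whether a participant with several reasons appears under each.
- **Other displays of add-on therapy exist.** A reader might take the 2.4.2 lipid tables to be the only ones. The general medication table works by preferred drug name, so commercial inclisiran recorded there would appear, though in the Inclisiran First column if grouped by actual treatment. Variable 23 covers add-on drugs in pooled form on the FAS.
- **Low crossover does little harm.** At 1% to 2%, 220 to 218 of 222 usual-care participants stay in their column, and the statin, ezetimibe, antibody and bempedoic acid rows nearly describe the randomized arm.
- **The tables are descriptive.** No test, estimate or decision rule uses them. Planned treatment is also defined in Table 2-1, so a version by randomized group can always be produced.

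What stands against this is that the SAP does not plan that version, and how far the planned one departs from the randomized arms depends on the crossover rate.

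**Conclusion.** The point holds in a limited form. On the natural reading of SAP 2.4.2 with 2.2 and Table 2-1, inclisiran use under Usual Care is zero by construction, the drug list has no inclisiran row, and no planned output shows post-baseline lipid-lowering therapy drug by drug by randomized arm. The number moved is 4 to 22 of 222 at an assumed 2% to 10% crossover. The documents say only that use will be minimal, so the actual distortion is unknown and grows with that rate. No primary test changes.

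Two stronger readings should be resisted. It is tempting to say that the tables cannot explain the LDL-C result; at low crossover they come close to the randomized arms, so the supportable statement is that they do not describe those arms exactly. It is also tempting to say that the most intensively treated usual-care participants are removed; the documents do not rank treatment intensity within usual care.

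A related discrepancy should be settled with this one. Protocol 12.1 groups the Safety Set by treatment received at randomization, under which a later commercial prescription would not, as I read it, move a participant. The SAP rule does, and SAP Section 4 does not list the change.

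**What to change.** In SAP 2.4.2:

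1. State that the lipid-lowering-therapy tables and both shift tables are produced on the FAS by randomized group. Keep the Safety Set for other concomitant medication.
2. Add a non-study inclisiran row to the drug list, and a matching add-on category in the shift table (`CMDECOD` contains 'inclisiran'), kept apart from sponsor-supplied doses.
3. Log the change in SAP Section 4, since Protocol 12.3 names the Safety Set. The same section already records moving medical history from the Safety Set to the FAS, so there is a precedent. Record there too the change in Safety Set grouping from Protocol 12.1.

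The cost is SAP wording and minor reprogramming of descriptive tables (population flag, treatment variable, one row and one category). No new data are needed: Table 2-1 and the Per-Protocol Set already depend on recorded inclisiran use.
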